3.6 Methods for ensuring blinding (Not applicable)

3.7 Methods for unblinding (Not applicable)

3.8 Restrictions

For a listing of concomitant medications see Section 7.7.

3.8.1 Grapefruit juice

The subject must not consume grapefruit juice while on olaparib therapy.

3.8.2 Contraception

Women of childbearing potential and their partners, who are sexually active, must agree to the use of 2 highly effective forms of contraception in combination (as described in Appendix E). This should be started from the signing of the informed consent and continue throughout the period of taking study treatment and for 1 month after the last dose of study medication, or they must totally/truly abstain from any form of sexual intercourse (as described in Appendix E).

For details of acceptable methods of contraception refer to Appendix E Acceptable Birth Control Methods.

3.8.3 Breastfeeding/lactation

Women are not permitted to breastfeed during this study. Lactating women can be eligible if they stop breastfeeding prior to the first dose of the study drug until at least 30 days after the last dose of the study drug.

3.9 Discontinuation of investigational product

Subjects may be discontinued from olaparib in the following situations:

- Subject decision. The subject is at any time free to discontinue treatment, without prejudice to further treatment;
- Adverse event;
- Severe non-compliance with the Clinical Study Protocol;
- Investigator determines it is in the best interest of the subject to discontinue study treatment;
- Bone marrow findings consistent with MDS/AML; or
- Objective progression according to RECIST v1.1 criteria.

3.9.1 Procedures for discontinuation of a subject from investigational product

At any time, subjects are free to discontinue olaparib or withdraw from the active treatment phase of the study (i.e., olaparib and assessments – see Section 3.10), without prejudice to further treatment. A subject who decides to discontinue olaparib will complete the Study Treatment Discontinuation Visit (see Section 4.2.5) and will be asked about the reason(s) for discontinuation and the presence of any adverse events. Adverse events will be followed-up (see Section 6), and all study medications should be returned by the subject.

By discontinuing from study treatment, the subject then enters the survival follow-up phase of the study. Subjects should be followed for progression (if discontinuation in the absence of progression) and survival following treatment discontinuation as per the study plan (see Section 4.3 and Table 6). Any subject who has not yet shown objective radiological disease progression at withdrawal from olaparib should continue to be followed as per RECIST v1.1.

Any subject discontinuing olaparib should be seen at 30 days post-discontinuation for the evaluations outlined in the study plan. The subject's tumor status should be assessed clinically, and, if appropriate, disease progression should be confirmed by radiological assessment via RECIST v1.1 criteria. After discontinuation of study medication, the Principal Investigator/Sub-Investigator will perform the best possible observation(s), test(s), and evaluation(s), as well as give appropriate medication and all possible measures for the safety of the subject. In addition, they will record in the electronic case report form (eCRF) the date of discontinuation, the reasons, manifestation, and treatment at the time of discontinuation. If a subject discontinues study treatment, the AstraZeneca Representative Study Physician must be informed immediately. The Subject will be required to attend the treatment discontinuation visit.

After discontinuation of the study medication at any point in the study, all ongoing adverse events or SAEs must be followed until resolution unless, in the Investigator's opinion, the condition is unlikely to resolve due to the subject's underlying disease, or the subject is lost to

follow-up (see Section 6.3.2). All new adverse events and SAEs occurring during the 30 calendar days after the last dose of study medication must be reported (if SAEs, they must be reported to AstraZeneca Safety representative **within 24 hours** as described in Section 6.4) and followed to resolution as above. Subjects should be seen at least 30 days after discontinuing study medication to collect and/or complete adverse event information. For guidance on reporting adverse events after the 30 day follow-up period see Section 6.3.1.1.

All subjects who received at least 1 dose of olaparib must be followed for progression and survival through the final analysis of all primary and secondary endpoints (approximately 6 months after the last subject has commenced study treatment [received at least 1 dose of olaparib]) + an additional 12 months after the data cut-off for follow-up for survival for applicable subjects. At the end of this additional 12 months of survival follow-up, updated OS and safety analyses will be conducted and the study will be closed. Subjects are, however, permitted to continue to receive olaparib beyond the closure of the database if, in the opinion of the Investigator, they are continuing to receive benefit from treatment with olaparib. During this time, adverse events of special interest and SAEs must still be collected and reported until 30 days after the subject finally stops taking olaparib. See Section 4.3.

If a subject is withdrawn from the study, see Section 3.10. See Section 3.10.2 for details on subject replacement.

For information regarding the withdrawal of consent for donated biological samples, see Section 5.6.9.

3.10 Criteria for withdrawal

Reasons for withdrawal from the study:

- Voluntary withdrawal by the subject who is at any time free to discontinue their participation in the study, without prejudice to further treatment (see Section 3.10.2);
- Incorrectly enrolled subjects (i.e., the subject does not meet the required inclusion/exclusion criteria for the study) (see Section 3.4);
- Subject lost to follow-up; or
- Death.

3.10.1 Screen failures

Screening failures are subjects who have signed informed consent and do not fulfill the eligibility criteria for the study, and therefore must not be enrolled.

3.10.1.1 Laboratory re-screening

If a subject is determined to be a screen failure on the basis of a laboratory results, during the screening period (28 days), the laboratory value may be rechecked to determine if the value

has changed to make the subject eligible. However, the 28-day screening period will not be extended.

3.10.2 Withdrawal of the informed consent

Subjects are free to withdraw from the study at any time (olaparib and assessments), without prejudice to further treatment.

A subject who withdraws consent will always be asked about the reason(s) and the presence of any adverse events. The Investigator will follow-up adverse events outside of the clinical study.

If a subject withdraws from participation in the study, her enrollment code cannot be reused. Withdrawn subjects will be replaced if the subject is withdrawn prior to the first post-baseline objective response assessment. Withdrawn subjects will not be replaced if the subject has had a post-baseline objective response assessment.

If a subject withdraws consent, they will be specifically asked if they are withdrawing consent to:

- Further participation in the study including any further survival follow-up (e.g., survival calls);
- Withdrawal of consent to the use of their study generated data; or
- Withdrawal to the use of any samples (see Section 5.6.9).

The status of ongoing, withdrawn (from the study), and "lost to follow-up" subjects at the time of an OS analysis should be obtained by the site personnel by checking the subject notes, hospital records, contacting the subject's general practitioner, and checking publicly available death registries. In the event that the subject has actively withdrawn consent to the processing of their personal data, the vital status of the subject can be obtained by site personnel from publicly available resources where it is possible to do so under applicable local laws.

For information regarding the withdrawal of consent for donated biological samples, see Section 5.6.9.

3.11 Discontinuation of the study

The study may be stopped if, in the judgment of AstraZeneca, study subjects are placed at undue risk because of clinically significant findings that:

- Meet individual stopping criteria or are otherwise considered significant;
- Are assessed as causally related to study medication; or
- Are not considered to be consistent with continuation of the study.

Regardless of the reason for study termination, all data available for the subject at the time of study discontinuation must be recorded in the eCRFs.

In terminating the study, the Sponsor will ensure that adequate consideration is given to the protection of the subjects' interests. See Section 9.3 for timelines for planned study completion.

4. STUDY PLAN AND TIMING OF PROCEDURES

This is a Phase II, open-label, non-randomized, multi-center cohort study assessing the efficacy and safety of olaparib tablets 300 mg CCl in subjects with platinum-sensitive or partially platinum-sensitive, relapsed, high-grade serous or high-grade endometrioid ovarian, fallopian tube, or primary peritoneal cancer, who have received at least 1 prior line of platinum-based chemotherapy.

The study will assess the effectiveness of olaparib tablets as measured by the ORRs as determined by RECIST v1.1, in subjects with gBRCAm, sBRCAm, or potential aberrations in HRD as determined by myChoice[®] HRD, as well as in subjects without identifiable HRD. This study will utilize Myriad BRACAnalysis CDx[®] for germline BRCA analysis and a tumor test (myChoice[®] HRD) for tumor BRCA analysis and HRD status. The Myriad testing may be submitted in advance of the 28-day screening window if the subject consents to the appropriate pre-screening informed consent form.

Four cohorts will be identified based upon genetic testing:

- Cohort 1: gBRCAm,
- Cohort 2: somatic BRCA mutated (sBRCAm) and germline BRCA wild type,
- Cohort 3: myChoice[®] HRD positive (genomic instability positive) and BRCA wild type (BRCAwt) (no BRCA mutation),
- Cohort 4: myChoice[®] HRD negative (genomic instability negative) and BRCAwt (no BRCA mutation).

For the cohort enrollment stopping rules, see Section 3.5 and Section 8.5.4.

This study consists of an up to 28-day screening period (Day -28 to Day -1) once the subject signs the main study consent. See Section 4.1.

Following the screening period, eligible subjects will enter the active treatment period of the study. Study visits will be conducted at Day 1 (Visit 2), Day 8 (Visit 3), Day 15 (Visit 4), Day 22 (Visit 5), Day 29 (Visit 6), and on Day 1 of a 4-week visit period up to 52 weeks (if not progressed and still on treatment), then on Day 1 of a 12-week visit period relative to date

of enrollment. For a list of specific procedures and assessments conducted during the active treatment period, see Section 4.2. When the subject discontinues olaparib, the Study Treatment Discontinuation Visit will be conducted (see Section 4.2.5).

Subjects should be discontinued from active study treatment phase if they have objective radiological disease progression according to RECIST v1.1 (see Appendix G) and complete the Study Treatment Discontinuation Visit as per the study plan.

A data cut-off for analysis of all primary and secondary endpoints will occur approximately 6 months after the last subject enrolled has commenced study treatment (received at least 1 dose of olaparib). The study will remain open for an additional 12 months after this data cut-off for survival follow-up for applicable subjects. At the end of this additional 12 months of survival follow-up, updated OS and safety analyses will be conducted and the study will be closed. Subjects are, however, permitted to continue to receive olaparib beyond the closure of the database if, in the opinion of the Investigator, they are continuing to receive benefit from treatment with olaparib. During this time, adverse events of special interest and SAEs must still be collected and reported until 30 days after the subject finally stops taking olaparib. See Section 4.3.2.

Assessments for survival will be made every 12 weeks (\pm 1 week) following objective radiological disease progression (RECIST v1.1). See Section 4.4.

A Follow-up Visit will be conducted 30 days after the discontinuation of olaparib (see Section 4.3.1).

Table 6

Study Plan – On Study Treatment and Discontinuation

Visit Number	1	2	3	4	5	6	Subsequent on treatment visits every 4 weeks ^a	Study treatment discontinued ^c	Follow-up 30 days after last dose of study	Overall Survival Follow-up ^e
							Tumor assessment visits every 8 or 12 weeks ^b		medication ^d	
							Visit No. 7 onwards			
Day	-28 to -1	1	8	15	22	29	Day 1 of next visit period ^f			
Visit Window			$\pm 3d$	$\pm 3d$	$\pm 3d$	$\pm 3d$	± 3d	+ 7d	± 7d	$\pm 7d$
Informed consent ^g	Х									
Demographics	Х									
Surgical and medical history	Х									
Prior cancer therapies including radiotherapy	Х									
Inclusion/exclusion criteria (history of blood transfusions) ^h	Х									
Enrollment		Х								
Physical examination i	Х	Х						Х		
Vital signs, body weight, height, (Includes BP, pulse, and temperature), and ECG ^{i, j}	Х	Х							Х	
ECOG performance status	Х	Х					Х	Х		
Hematology/clinical chemistry ^k	Х	Х	Х	Х	Х	Х	Х	Х	Х	
Urinalysis	Х									

Table 6

Study Plan – On Study Treatment and Discontinuation

Visit Number	1	2	3	4	5	6	Subsequent on treatment visits every 4 weeks ^a Tumor assessment visits every 8 or 12 weeks ^b Visit No. 7 onwards	Study treatment discontinued ^c	Follow-up 30 days after last dose of study medication ^d	Overall Survival Follow-up °
Day	-28 to -1	1	8	15	22	29	Day 1 of next visit period ^f			
Visit Window			$\pm 3d$	$\pm 3d$	$\pm 3d$	$\pm 3d$	± 3d	+ 7d	$\pm 7d$	± 7d
Pregnancy test ¹	Х	Х				Х	Х		Х	
Blood sample for determination of BRCA status via Myriad ^{m,n}	Х									
Blood sample for disease specific marker (CA-125) °		Х				Х	Х	Х		
Tumor Assessment (CT or MRI according to RECIST v1.1)	X ^p	st (± 1	Every 8 weeks (± 1 week) from receipt of first dose of study drug (Visit 2) for 48 weeks and every 12 weeks (± 1 week) thereafter until PD has been determined by the Investigator according to RECIST v1.1 criteria (including confirmatory RECIST scan).							
Adverse events (continuous from the time of informed consent) ^q	Х	Х	Х	Х	Х	Х	Х	Х	Х	
Concomitant medications including blood transfusions	Х	Х	Х	Х	Х	Х	Х	Х	Х	
Olaparib dispensed/returned r		Х				Х	Х	Х		

Table 6

Study Plan - On Study Treatment and Discontinuation

Visit Number	1	2	3	4	5	6	Subsequent on treatment visits every 4 weeks ^a Tumor assessment visits every 8 or 12 weeks ^b Visit No. 7 onwards	Study treatment discontinued ^c	Follow-up 30 days after last dose of study medication ^d	Overall Survival Follow-up °
Day	-28 to -1	1	8	15	22	29	Day 1 of next visit period ^f			4
Visit Window			± 3d	+ 7d	± 7d	± 7d				
Subsequent cancer therapy following discontinuation of study treatment ^s									Х	
Blood sample for pharmacogenetics (mandatory) ^t		X								-
Tumor sample (mandatory) ^m , n,u,v	Х									
CCI										
The second secon										
										X

a. Visit to take place on Day 1 of a 4-week visit period up to 52 weeks (if not progressed and still on treatment), then on Day 1 of a 12-week visit period relative to date of enrollment until PD (RECIST v1.1).
b. Follow-up assessments will be performed at the end of every 8 weeks (± 1 week) up to 48 weeks, then every 12 weeks (± 1 week) relative to date of enrollment until PD (RECIST v1.1).
b. Follow-up assessments will be performed at the end of every 8 weeks (± 1 week) up to 48 weeks, then every 12 weeks (± 1 week) relative to date of enrollment until PD (RECIST v1.1).

Date 10 October 2017

- chest or upper abdomen lymphadenopathy at baseline), abdomen, and pelvis with any other regions imaged at baseline where disease was present. Any other sites at which new disease is suspected should also be appropriately imaged. Subjects must be followed until RECIST PD. If an unscheduled assessment was performed and the subject has not progressed, every attempt should be made to perform the subsequent assessments at their scheduled visits. Subjects who are determined to have PD according to RECIST v1.1 criteria (including confirmatory RECIST scan) by the Investigator may have additional scans performed per the site's standard of care. Scans will be collected through disease progression.
- c. Subjects should be discontinued from study treatment if they have objective radiological disease progression according to RECIST v1.1 (see Appendix G) and complete the Study Treatment Discontinuation Visit as per the study plan.
- d. During the follow-up period, subjects will be followed for PFS (CA-125 and radiographic evidence of progression per site standards) until database lock/end of study, and assessed for overall survival.
- e. Assessments for survival should be made every 12 weeks (± 1 week) following disease progression. Survival information may be obtained via telephone or email contact with the subject's family, or by contact with the subject's current physician.
- f. Visit 7 equals Day 57 (Week 8), then Visit 8 equals Day 85 (Week 12), etc.
- g. Informed consent for pre-screening will be taken specifically for myChoice[®] HRD (central Myriad HRD tumor) and BRACAnalysis CDx[®] (gBRCA testing). A separate informed consent needs to be signed to begin study procedures for the overall study.
- All inclusion/exclusion criteria including history of blood transfusion within previous 120 days from informed consent and the reasons (e.g., bleeding or myelosuppression).
- Height will only be recorded at screening. Temperature and weight only required if clinically indicated. Physical examination should be performed according to the schedule; after the baseline assessment it is not necessary to record the details on an eCRF unless related to an adverse event/SAE. Any clinically significant changes should be recorded as adverse events.
- j. The ECG at screening should be performed within 7 days prior to starting the study treatment. Electrocardiograms should be performed once the subject has been in the supine position for at least 5 minutes in each case.
- k. Coagulation tests are only required if clinically indicated. For a list of all required laboratory tests, please refer to Section 5.2.1. All enrolled subjects will have safety blood samples taken weekly during the first month on treatment followed by monthly assessments until discontinuation of study treatment. Safety blood samples will be taken at the 30-day Follow-up Visit as well.
- 1. Women of childbearing potential must have a negative urine or serum pregnancy test within 28 days prior to starting treatment and a confirmatory test on Day 1 before initiating olaparib treatment; and at the timepoints shown in Table 6 during study treatment, and at the 30 day follow up visit. Pregnancy testing for women of childbearing potential should be conducted at regular intervals (eg, monthly). If results are positive, the subject is ineligible/must be discontinued from the study.
- m. Subjects with an unknown gBRCA status will have their blood and tumor tested with the myChoice[®] HRD and BRACAnalysis CDx[®] in parallel at pre-screening (if consented) or at screening, if not previously performed by Myriad during pre-screening.
- n. Subjects with known gBRCA status from the local laboratory must provide a blood and tumor sample at screening for confirmatory purposes. Their involvement in the study will not be affected by the result of the Myriad test.
- CA-125 will be tested at baseline and every month thereafter until objective disease progression, based on progressive serial elevation of serum CA-125 according to the modified GCIG criteria. Samples should be taken pre-dose at Visit 2.
- p. RECIST assessments will be performed using CT/MRI of the chest, abdomen, and pelvis, with other regions as clinically indicated for the assessment of disease, no more than 28 days prior to study treatment start and as close as possible to the start of study treatment. A CT examination with intravenous contrast media administration is the preferred method. An MRI should be used where CT is not feasible or it is medically contraindicated.

Date 10 October 2017

- q. When an adverse event for nausea and vomiting occurs, an additional eCRF will require completion. All ongoing adverse events/SAEs and any new adverse events/SAEs identified during the 30 calendar day follow-up period after last dose of study medication must be followed to resolution (or stabilization or return to baseline). A targeted questionnaire will be sent to any Investigator reporting an AESI as an aid to provide further detailed information on the event.
- Sufficient olaparib should be dispensed for at least each active treatment period plus overage; however, additional treatment can be dispensed to subjects to last longer in accordance with local practice.
- s. All anti-cancer treatments (including, but not limited to, chemotherapy and targeted agents), and the Investigator's opinion of response to them plus the date of progression, post-discontinuation of study treatment, need to be recorded.
- t. Only 1 sample should be collected per subject for pharmacogenetics during the study. The sample should be taken pre-dose.
- u. Subjects must provide a tumor sample to be considered for the study the sample can either be an archival sample or a new baseline tumor sample. If a tumor sample is taken at pre-screening for Myriad testing a sample will not need to be re-taken for Myriad testing; independent of the tumor sample for Myriad testing, an additional sample must be provided at screening for future research purposes.
- v. The biopsied tumor should not be assessed as a target lesion as part of the RECIST assessments if there are other lesions available. The biopsy should be taken after the baseline scan has been performed.

CCI		

AESI = adverse event of special interest; BP = blood pressure; CA = Cancer antigen; CT = computed tomography; CC

ECG = electrocardiogram; ECOG = Eastern Cooperative Oncology Group; eCRF = electronic case report form; gBRCA = germline BRCA; GCIG = Gynecological Cancer Intergroup; HRD = homologous recombination deficiency; MRI = magnetic resonance imaging; No. = number; PD = progressive disease; PFS = progression-free survival; RECIST = Response Evaluation Criteria in Solid Tumors; SAE = serious adverse event.

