4.2.4 Study Visit 7, Day 57, and every 4 weeks onwards

Subsequent on-treatment visits for the active treatment period will take place on Day 1 of a 4-week visit period up to 52 weeks (if not progressed and still on treatment), then on Day 1 of a 12-week visit period relative to date of enrollment until PD (RECIST v1.1). Subsequent on-treatment visits for subjects who remain on treatment post-progression should take place every 12 weeks. Tumor assessment visits will be performed at the end of every 8 weeks (± 1 week) up to 48 weeks, then every 12 weeks (± 1 week) relative to date of enrollment until PD (RECIST v1.1). Subjects will be contacted to assess for survival every 12 weeks following disease progression until death, withdrawal of consent, or study closure. See Section 4.4.

The following procedures will be performed at Visit 7, Day 57 (\pm 3 days) and every 4 weeks onward (i.e., Visit 8 [Day 85], Visit 9 [Day 113], etc.) through the active treatment period:

- Assess functional status using the ECOG performance status scale (see Appendix F);
- Obtain blood sample for hematology/clinical chemistry (see Section 5.2.1 and Table 8);
- Obtain blood sample for disease specific marker (CA-125) (see Section 5.2.1.4 and Table 8);
- Assess tumor (CT or MRI according to RECIST v1.1) (see Section 5.1.1);
- Note: The tumor assessments according to RECIST v1.1 will be performed every 8 weeks (± 1 week) from the first dose of study drug (Visit 2) for 48 weeks, and then every 12 weeks (± 1 week) (relative to the date of enrollment) thereafter until determined by the Investigator according to RECIST v1.1 criteria (including confirmatory RECIST scan).
- Assess and record concomitant medications including blood transfusions;
- Assess subject for adverse events (continuous from time of informed consent); and
- Dispense/return olaparib.

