5.2.1 Laboratory safety assessments

Blood and urine samples for determination of clinical chemistry, hematology, coagulation, and urinalysis will be taken at the times indicated in the study plan (see Table 6). Note: Safety blood samples (e.g., clinical chemistry, hematology, coagulation, etc.) do not need to be repeated on Visit 2 (Day 1) of the study treatment if assessed at least 3 weeks after the last dose of chemotherapy but within 7 days before starting study treatment, unless the Investigator believes the values are likely to have changed significantly.

Additional safety samples (e.g., clinical chemistry, hematology, coagulation, etc.) may be collected if clinically indicated at the discretion of the Investigator. The date, time of collection, and results (values, units, and reference ranges) will be recorded on the appropriate eCRF.

The clinical chemistry, hematology, and urinalysis will be performed at a local laboratory at or near to the investigative site. Sample tubes and sample sizes may vary depending on laboratory method used and routine practice at the site.

The following laboratory variables will be measured:

Table 7	Laboratory Safety Variables
---------	-----------------------------

Hematology/Hemostasis (whole blood)	Clinical Chemistry (serum or plasma)
B-Hemoglobin	S/P-Creatinine
B-Leukocyte count	S/P-Bilirubin, total
B- Leukocyte differential count (absolute count)	S/P-Alkaline phosphatase
B-Platelet count	S/P-Aspartate transaminase
B-Absolute neutrophil count	S/P-Alanine transaminase
	S/P-Albumin
Urinalysis (dipstick)	S/P-Potassium
U-Hb/erythrocytes/blood	S/P-Calcium, total
U-Protein/albumin	S/P-Sodium
U-Glucose	S/P-Urea or blood urea nitrogen

B = blood; P = plasma; S = serum; U = urine.

The Investigator should make an assessment of the available results with regard to clinically relevant abnormalities. The laboratory results should be signed and dated and retained at the site as source data for laboratory variables. For information on how adverse events based on laboratory tests should be recorded and reported, see Section 6.3.

In case a subject shows an AST or $ALT \ge 3 \times ULN$ or $TBL \ge 2 \times ULN$, please refer to Appendix D, for further instructions.

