5.2.1.4 Disease specific tumor marker samples (CA-125)

As part of the routine safety blood samples, all subjects will supply blood samples for CA-125 (2 mL) assessment at the beginning of each 4-week period prior to the subject receiving study treatment.

It is important to follow the assessment schedule as closely as possible. If CA-125 assessment is performed outside of the scheduled visit \pm 1-week window interval, every attempt should be made to assess the CA-125 at the scheduled time points. Subjects will be evaluated until objective disease progression (RECIST v1.1), based on progressive serial elevation of serum CA-125 according to the modified GCIG criteria. For the modified GCIG criteria, see Appendix H.

Further assessment of CA-125 post-serological progression will be at the discretion of the Investigator according to local clinical practice.

Objective response rates based on the Investigator review of RECIST v1.1, CA-125 response rates, and the percentage of subjects who had a RECIST response and/or a CA-125 response will be summarized.

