8.4.3.5 Time to earliest progression by RECIST or CA-125, or death

The CA-125 progression will be based upon the latest GCIG guidelines. Progression or recurrence based on serum CA-125 levels will be defined on the basis of a progressive serial elevation of serum CA-125 according to the following criteria:

- Subjects with elevated CA-125 pre-treatment and normalization of CA-125 must show evidence of CA-125 \ge 2 × ULN on 2 occasions at least 1 week apart;
- Subjects with elevated CA-125 before treatment, which never normalizes, must show evidence of CA-125 \geq 2 times the nadir value on 2 occasions at least 1 week apart; or
- Subjects with CA-125 in the reference range before treatment must show evidence of CA-125 \ge 2 × ULN on 2 occasions at least 1 week apart.

Cancer antigen-125 progression will be assigned the date of the first measurement that meets the criteria as noted. Subjects are not evaluable for CA-125 if they have received mouse antibodies (unless the assay used has been shown not to be influenced by human anti-mouse antibody) or if there has been medical and/or surgical interference with their peritoneum or pleura (e.g., paracentesis) during the previous 28 days.

For the purpose of this endpoint, a subject may be declared to have PD on the basis of either the objective RECIST v1.1 criteria or the GCIG CA-125 criteria. The date of progression will be the date of the earlier of the 2 events if both are documented.

Time to earliest progression is defined as the time from the date of the first dose of olaparib until the earliest of CA-125 progression or RECIST progression, or death from any cause. Subjects without a CA-125 progression or objective radiological progression by RECIST v1.1 who are still alive at the time of analysis will be censored at their last evaluable RECIST assessment or their last available CA-125 measurement, whichever is the most recent at the time of analysis. If a subject progresses or dies after 2 or more missed RECIST and CA-125 assessments, then the subject will be censored at the time of their last evaluable assessment.

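### After week 52 on-treatment visits move to every 12 weeks, but safety bloods and CA-125 stay monthly or 4-weekly, so about two of every three second-year blood samples have no scheduled visit

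*Protocol*

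**What the plan says.** **Visits.** Table 6 footnote a sets visits every 4 weeks up to week 52, "then on Day 1 of a 12-week visit period relative to date of enrollment until PD". Section 4 and the first paragraph of Section 4.2.4 say the same.

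**Safety bloods.** Table 6 footnote k, attached to the hematology/chemistry row, requires "safety blood samples taken weekly during the first month on treatment followed by monthly assessments until discontinuation of study treatment".

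**CA-125.** The Table 6 CA-125 footnote says: "CA-125 will be tested at baseline and every month thereafter until objective disease progression". Section 5.2.1.4 asks for "assessment at the beginning of each 4-week period prior to the subject receiving study treatment". The same section leaves CA-125 testing after serological progression to the investigator.

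**Procedure list in 4.2.4.** ECOG status, hematology/chemistry, CA-125, adverse-event review and dispensing are to be done at Visit 7 "and every 4 weeks onward (i.e., Visit 8 [Day 85], Visit 9 [Day 113], etc.) through the active treatment period".

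**Where bloods are tested.** Section 5.2.1 states: "The clinical chemistry, hematology, and urinalysis will be performed at a local laboratory at or near to the investigative site". It refers the reader to Table 6 for sample timing. Table 8 marks CA-125 as locally assessed.

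**Use of CA-125.** TTAP counts CA-125 progression as an event, and Section 8.4.3.5 adds: "Cancer antigen-125 progression will be assigned the date of the first measurement that meets the criteria as noted".

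**The concern.** The blood-sampling rules in footnote k, the CA-125 footnote and the 4.2.4 list do not change at week 52, but the visit schedule that should deliver them does. Section 4.2.4 contradicts itself: its first paragraph goes to 12-weekly visits, while its list keeps every procedure 4-weekly. Section 5.2.1 does not settle the matter, because the table it points to carries both rules. Nothing in the protocol text at hand schedules laboratory-only draws between the later visits.

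The main stake is safety. Section 1.3.3 lists anemia, neutropenia and thrombocytopenia among the common effects of olaparib. A site working from the visit schedule would stretch routine counts threefold. Section 5.2.1 allows extra samples when clinically indicated, and Section 6.7.1.3 requires weekly counts after a prolonged interruption, but both start only once a problem has been noticed. A cytopenia without symptoms is found by the routine count.

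A smaller stake is consistency of TTAP: sites that resolve the conflict differently would date the same CA-125 progression differently.

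**Working it through.** The protocol states no number of second-year samples or visits, so there is no figure to reproduce. As a check on the calendar, Day 1 + 28k for k = 2, 3, 4 gives Days 57, 85 and 113, which match the days given for Visits 7, 8 and 9.

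**Samples against visits, after week 52 to week 104**

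- 4-weekly samples: weeks 56, 60, …, 104, which is (104 − 56)/4 + 1 = 13.
- 12-weekly visits counted from enrollment: weeks 60, 72, 84, 96 = 4.
- 12-weekly visits counted from week 52: weeks 64, 76, 88, 100 = 4.
- Samples without a visit: 13 − 4 = 9 under either anchor (69%).

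Other readings change this little:

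| Reading | Samples | On a visit | Without a visit |
|---|---|---|---|
| 4-weekly, weeks 56 to 104 | 13 | 4 | 9 (69%) |
| Calendar-monthly | 12 | 4 | 8 (67%) |
| 4-weekly, weeks 52 to 100, visits counted from week 52 | 13 | 5 | 8 (62%) |

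**Gap between routine counts.** 12 × 7 = 84 days on the visit schedule, against 4 × 7 = 28 days under the sampling rule.

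**Delay in dating CA-125 progression after week 52.** If the rise falls evenly between samples, the mean wait for the next sample is half the interval: 4/2 = 2 weeks or 12/2 = 6 weeks, a difference of about 4 weeks. A simulation with exponential times (medians 5 to 9.2 months) gave 2.0 and 5.9 weeks with visits counted from enrollment, a mean difference of 3.8 to 3.9 weeks. With visits counted from week 52 the difference was 4.2 to 4.3 weeks. The largest delay with enrollment-based visits is 12 − 4 = 8 weeks.

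**How many subjects.** The protocol does not give this, so only a rough upper guide is possible. Assume that time on treatment follows an exponential PFS curve. Week 52 is 11.96 months, and the share still on treatment is 0.5^(11.96/median).

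- Median 5 months (assumed): 0.191 × 300 = 57.
- Median 7 months (Study 42, Section 1.1): 0.306 × 300 = 92.
- Median 9.2 months (platinum-sensitive subgroup of Study 12, Section 1.3.2.1): 0.406 × 300 = 122.

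The last two medians come from germline BRCA-mutated patients, so they are likely to be too long for the BRCA wild-type cohorts. All three counts ignore stopping for toxicity or by choice.

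**The case against.** The strongest reply is that the required interval is not in doubt. Footnote k is mandatory and sits on the laboratory row itself. The Table 6 column header and the title of 4.2.4 also say every 4 weeks. A visit interval and a sampling interval can coexist, and the tests are local, so a careful site could arrange draws between visits. A site that checked counts every 84 days would be breaching footnote k. The laboratory manual, the blacked-out part of Section 6.7 or Appendix H, none of which is at hand, might also schedule interim draws.

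This narrows the point to a wording fault but does not remove it. Three places tell the site when to see the subject, none mentions draws in between, and one list ties the bloods to a full visit. The protocol itself should not depend on a site noticing that one footnote overrides another.

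On CA-125 most of the objection stands. A reader might infer that rises between scans would go undated. They would not: they would be dated at the next sample. A reader might infer that later CA-125 samples always coincide with scans. That depends on whether the 12-week periods run from enrollment or from week 52. A longer wait for the confirming reading does not move the event date, which is that of the first qualifying value, and Section 8.4.3.5 needs only 1 week between readings. Nor is monthly CA-125 clearly required of everyone in the second year, since 5.2.1.4 makes it discretionary after serological progression.

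**Conclusion.** The contradiction is in the current text and should be corrected, chiefly for safety monitoring. About two of every three required second-year safety samples have no scheduled visit: 9 of 13 if 4-weekly, 8 of 12 if calendar-monthly. Following the visit schedule would lengthen the gap between routine blood counts from about 28 to 84 days. This rests only on counting the schedule, not on any efficacy assumption.

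The effect on TTAP is minor. It reaches only subjects still free of both CA-125 and RECIST progression after week 52. For them CA-125 progression would be dated about 4 weeks later on average, and at most about 8 weeks later with visits counted from enrollment. The delay matters less where RECIST progression comes first. TTAP is a descriptive secondary endpoint. ORR, the sample size and any median TTAP before week 52 do not change, so the documents do not support a claim that the efficacy results are compromised.

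The counts of 57 to 122 of 300 subjects are an upper guide only. They use PFS as a proxy for time on treatment and should not be read as the number affected for TTAP, where anyone with earlier CA-125 progression already has an event.

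**What to change.** In Table 6 footnote a, Section 4 and Section 4.2.4, state that after week 52:

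- hematology and clinical chemistry continue every 4 weeks until treatment discontinuation;
- CA-125 continues every 4 weeks until CA-125 (GCIG) progression or objective progression, whichever is first, with later CA-125 at the investigator's discretion as in 5.2.1.4;
- both are taken by local laboratory draw between the 12-weekly clinic visits;
- the other items in the 4.2.4 list, such as ECOG status and dispensing, are limited to the 12-weekly visits.

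The stop at CA-125 progression matters: an instruction to continue to objective progression for everyone would conflict with 5.2.1.4.

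The cost is a few lines in one amendment and about 8 to 9 local draws per subject in the second year between clinic visits. Footnote k already requires these draws, and no clinic visits are added.
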